#### 9.6.2 Secondary Analyses

Similar to the initial primary analysis regression model, changes in other outcome measures will be compared between the Visbiome Extra Strength and placebo arms by linear regression. For these models each participant will have a single outcome measure of change from baseline to week 26. The only predictor variable will be study arm.

The weeks 26 and 38 levels of the primary, secondary, and exploratory outcome measures will be compared with baseline levels through linear regression.

Spearman correlations will be used to evaluate correlations between changes in select outcome measures. In addition, longitudinal changes in these measures will be examined using graphical approaches, descriptive statistics, and possibly repeated measures modeling.

Safety will be evaluated by summarizing the nature and rate of AEs within each study arm for all participants initiating study product. Comparisons of overall and AE-specific grades between study arms will be evaluated with an exact test for ordered categorical data (Wilcoxon rank-sum test of the maximum grade for each participant). Study product tolerability will be evaluated by summarizing study product modifications and discontinuations by study arm.

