2.8.1 Hypotheses

- I. After administration of Visbiome Extra Strength, other markers of systemic inflammation interleukin (IL)-6, interferon gamma-induced protein (IP)-10, soluble tumor necrosis factor receptor I (sTNF-RI), soluble CD163 (sCD163), oxidized low-density lipoprotein (LDL), kynurenine to tryptophan (KT) ratio, and coagulopathy (D-dimer) will decrease.
- II. After administration of Visbiome Extra Strength, markers of microbial translocation lipopolysaccharide (LPS) and lipopolysaccharide-binding protein (LBP) will decrease.
- III. After administration of Visbiome Extra Strength, peripheral CD4+ lymphocyte counts and CD4+/CD8+ ratio will increase.
- IV. After administration of Visbiome Extra Strength, markers of lymphocyte and monocyte activation and senescence will decrease.
- V. Visbiome Extra Strength administration will increase gastrointestinal microbial diversity in fecal samples.
- VI. After administration of Visbiome Extra Strength, markers of enterocyte death as measured by I-FABP (intestinal fatty acid binding protein) will decrease.
- VII. Visbiome Extra Strength will be safe and well tolerated.
- VIII. The gut microbiome changes will persist after completion of Visbiome Extra Strength administration.

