4.4 Statistical Summaries and Testing

All statistical tests will be two-sided with a nominal alpha level of 0.05 and no adjustment for multiple testing.

Specimens collected 1 day after the last dose of study treatment will be considered "on treatment".

Specimens collected within 6 days of an influenza vaccination will not be used for analysis unless the vaccination and specimen collection occurred on the same date and the site has documented that the vaccination was given after specimen collection.

Outcome measures will be transformed for analyses and summaries on the log₁₀ scale, as appropriate, if determined to not be approximately normally distributed.

Because the stratification is to ensure balance between the treatment arms within A5352s and is not felt to affect A5350 outcomes, the stratification will not be taken into account in analyses.

Safety analyses will summarize the highest grade AE by participant using the mITT population and will compare treatment arms using the Wilcoxon rank-sum test. All AEs and AEs related to study treatment will be analyzed.

For all continuous outcome measures, tabular and graphical data summaries will be provided for both cross-sectional values across study weeks and change from baseline to post-baseline study weeks and will use the PP population. Mean changes in outcome measures will be compared between arms with either a two-sample t-test with equal variances or an adjusted linear regression model, as appropriate. The mean difference and 95% confidence interval (CI) will be provided along with the associated p-value.

For the primary analysis, two supplemental linear regression analyses will be performed. The first will additionally adjust for baseline sCD14 values (continuous) while the second will assess differential Visbiome Extra Strength

effects by baseline sCD14 tertile by additionally adjusting for the sCD14 tertile main effect and the study arm by sCD14 tertile interaction.

Correlations will be assessed with scatter plots as well as the Spearman correlation coefficient and associated p-value using the PP population.

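### The between-arm safety analysis gives a rank-test p-value on highest AE grade but no interval for any AE proportion or difference, so a non-significant result cannot show what excess harm is excluded

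*SAP*

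**What the plan says.** The design statements (protocol Schema, SAP 2.1) make safety and tolerability an aim alongside sCD14. Hypothesis VII in SAP 2.8.1 reads: "Visbiome Extra Strength will be safe and well tolerated". Protocol 9.2.2.7 makes product-related AEs of Grade 3 or higher the safety outcome. SAP 3.2 lists the occurrence of AEs more broadly.

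On analysis, SAP 4.4 takes each participant's highest AE grade in the mITT population and "will compare treatment arms using the Wilcoxon rank-sum test". It adds: "All AEs and AEs related to study treatment will be analyzed". Protocol 9.6.2 has the same test in exact form and extends it to individual AE types: "Comparisons of overall and AE-specific grades between study arms will be evaluated with an exact test for ordered categorical data".

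Description is planned as well. Protocol 9.6.2 says: "Safety will be evaluated by summarizing the nature and rate of AEs within each study arm for all participants initiating study product" and "Study product tolerability will be evaluated by summarizing study product modifications and discontinuations by study arm". Protocol 9.6 adds counts and types of product-related AEs and the proportion who stop product.

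The SAP's one commitment to an interval is in the paragraph of 4.4 on continuous outcomes: "The mean difference and 95% confidence interval (CI) will be provided along with the associated p-value". Protocol 9.4 likewise tabulates power and CI width for continuous secondary endpoints only. Neither document gives an expected AE rate, a safety margin or a bound.

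**The concern.** The rank-sum test asks whether the two arms have the same distribution of highest grade. It can give evidence of harm. It cannot give evidence that harm is absent, because with 45 per arm a non-significant result is likely under both no effect and a sizeable one. Hypothesis VII is a statement of the second kind.

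What a reader needs in order to judge it is an estimate of the excess risk and the largest excess the data do not rule out. The plan supplies that for biomarkers and not for AEs. Nor does a p-value on mixed grades estimate the quantity in protocol 9.2.2.7, which is the proportion with a related Grade ≥3 event.

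At stake is how the safety result can be worded. Without an interval, the report will hold by-arm counts and a p-value, and nothing in the plan says what a large p-value does and does not mean.

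**Working it through.** **Inputs from the documents.** 45 per arm (SAP 2.3). Safety population: randomised participants who started product, so at most 45 per arm (SAP 4.1). Two-sided alpha 0.05 with no multiplicity adjustment (SAP 4.4). **Assumed:** the Grade ≥3 AE rates, because the documents give none; a range is shown.

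**The plan's own figure.** The sample size was set for sCD14: difference 0.07, SD 0.09, 90% power. A two-sample t-test with 36 per arm has power 0.902, and 36/0.8 = 45. So protocol 9.4 reproduces. There is no corresponding safety figure to reproduce.

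**Chance of missing a doubling.** Score each participant as Grade ≥3 yes or no. With i events on placebo and j on active, and m = i + j, the tie-corrected Wilcoxon statistic reduces to

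z = (j − i) / √(m(90 − m)/89).

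The exact version is Fisher's test. Power is the sum, over all i and j, of Bin(i; 45, p₀) × Bin(j; 45, p₁) for the pairs with p ≤ 0.05. The miss rate is 1 − power.

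| Assumed placebo vs active | Power, asymptotic | Power, exact | Miss rate |
|---|---|---|---|
| 5% vs 10% | 0.130 | 0.057 | 87–94% |
| 10% vs 20% | 0.272 | 0.179 | 73–82% |
| 15% vs 30% | 0.398 | 0.304 | 60–70% |
| 20% vs 40% | 0.547 | 0.464 | 45–54% |
| 25% vs 50% | 0.686 | 0.625 | 31–37% |

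The span within a row is the difference between the two forms of the test. The uncertainty about AE rates is the difference between rows.

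**Effect of lower grades.** Suppose lower grades are also recorded and keep the same relative frequencies among participants without a Grade ≥3 event. On a five-level scale, simulation of the asymptotic test gives miss rates of about 86–87% at 10% vs 20%, 74–76% at 15% vs 30% and 59–61% at 20% vs 40%. This may overstate the dilution here. Under protocol 6.3.1.3 and 6.3.1.4, signs, symptoms and laboratory toxicities below Grade 3 are logged only if they changed treatment, while the listed diagnoses in 6.3.1.2 carry no grade threshold. The yes/no table is therefore used as the main result.

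**What an interval would show.** The approximate 95% half-width for a risk difference is 1.96 × √(p₀(1 − p₀)/45 + p₁(1 − p₁)/45):

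- 10% vs 10%: 1.96 × √0.00400 = ±12.4 points
- 10% vs 20%: 1.96 × √0.00556 = ±14.6 points
- 20% vs 20%: 1.96 × √0.00711 = ±16.5 points

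As an illustration, take 5/45 on placebo and 9/45 on active. Then z = 4/√(14 × 76/89) = 1.157, so p = 0.25 (exact test 0.38). The risk difference is 8.9 points, with approximate 95% CI −6.0 to +23.8. The p-value alone says only that no difference was shown. The interval says that an excess of more than 20 points remains possible.

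With no events among 45 exposed, the exact two-sided 95% upper limit for the rate is 1 − 0.025^(1/45) = 7.9%.

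**The case against.** The strongest reply is that this is a phase II trial sized for a biomarker, with safety as a secondary and largely descriptive matter. AE rates, product modifications and discontinuations will be shown by arm, the monitoring committee sees AEs by arm every six months (protocol 9.5, SAP 2.11.2), and anyone with n/N can compute an interval. Low power for uncommon events is inherent at this size, and an interval does not cure it.

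Much of this stands. The descriptive plan is real and sensible, and the missing element is small. What remains is that the plan goes beyond description by specifying a significance test for AEs, and gives that test no accompanying estimate of uncertainty. An interval does not add power, but it displays the lack of it, which a p-value conceals.

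A reader might go further and infer that p>0.05 will be taken as proof of safety. The documents do not say so: no rule links the Wilcoxon result to hypothesis VII, and being safe and well tolerated is nowhere defined as equality with placebo. A reader might also infer that the p-value is the only between-arm evidence on safety. The by-arm summaries in protocol 9.6.2 and SAP 4.4 contradict that.

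**Conclusion.** The point holds as a gap in the analysis plan that is cheap to close. The sole inferential safety method is a test of no difference in highest AE grade, and no AE proportion or difference is given an interval. A non-significant result at 45 per arm therefore cannot support hypothesis VII.

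The size depends on AE rates that the documents do not state. Over assumed control rates of 5% to 25%, a doubling of Grade ≥3 AEs is missed between about 31% and 94% of the time, and at least 60% of the time when the control rate is 15% or lower. No single row of the table should be quoted as a property of the test. The figures assume all 45 per arm start product and a yes/no scale; fewer starters would raise the miss rates.

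This is not an error in the sample size, and it gives no ground for saying that the sponsor intends to treat non-significance as safety. It affects how the safety result is reported and worded, not the sCD14 analysis.

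**What to change.** Amend the safety paragraph of SAP 4.4 as follows.

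1. For participants with any Grade ≥3 AE, and for those with any product-related Grade ≥3 AE, in the mITT population, report n/N per arm with an exact 95% CI, and the risk difference (active minus placebo) with its 95% CI. Name the interval method in advance. A score-type interval is preferable to the simple approximation used above, which collapses to zero width if neither arm has an event.
2. State that safety will be interpreted by the upper limit of the risk-difference interval, that is, the largest excess the data do not exclude.
3. Keep the Wilcoxon p-value as descriptive, and state that p>0.05 will not be taken as evidence for hypothesis VII.

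This needs a few sentences and one or two extra table columns, with no new data. The downside is that the interval will be wide, about ±12 to ±17 percentage points at rates of 10–20%, so the safety statement becomes more modest.

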#### 6.2.4 Discontinuation Evaluations

# Evaluations for Randomized or Registered Participants Who Do Not Start Study Treatment

All CRFs must be completed and keyed for the period up to and including week 2.

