#### Premature Treatment Discontinuation Evaluations

Participants who prematurely permanently discontinue study treatment will be followed on study/off study treatment per the SOE.

Site personnel should notify the protocol core team via e-mail ([contact]) within 48 hours of any participant who prematurely discontinues study product.

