# 9.6 Analyses

All statistical tests will be two-sided with a nominal alpha level of 0.05. Because this is a phase II study and all potential biologic activities of the intervention are of interest, analyses will be as-treated, and limited to participants who 1) have baseline and week 26 sCD14 measurements, 2) remain on study product through week 26 (participants with more than 50% on average of missed study product may be excluded), 3) have not used prohibited medications, 4) do not have a confirmed virologic failure (as defined per section 6.2.3 at or prior to week 26, and 5) do not experience inflammatory conditions, receive vaccines, or have concurrent illness (as defined per section 6.2.3).

NOTE: Participants experiencing inflammatory conditions at the time of a visit are instructed to wait 7 days before measurements are obtained. Measurements obtained while inflammatory conditions are present will not be included in the analysis. A supplemental intent-to-treat analysis will also be performed and will include all randomized participants. No adjustment for multiple testing will be performed. A summary of the number of participants experiencing study product-related AEs and the types of AEs will be reported, as will the proportion of participants who discontinue study product after entry.

To reduce intra-participant variability, two blood draws will be performed at baseline (entry and week 2) and week 26 (week 25 and week 26) and the measurements will be the average of two for sCD14. If repeat measurements are not available at either of these time points, a single measurement will be used rather than the average.

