#### 9.6.1 Primary Analysis

The primary objective of the study is to assess the effect of Visbiome Extra Strength on sCD14 in HIV-infected participants well-controlled on ART. To address this, changes in sCD14 from baseline to week 26 will be compared between the Visbiome Extra Strength arm and the placebo arm by linear regression. For this model each participant will have a single outcome measure of sCD14 change from baseline to week 26. The only predictor variable will be study arm.

Two supplemental linear regression analyses will be performed. The first will additionally adjust for baseline sCD14 values (continuous) while the second will assess differential Visbiome Extra Strength effects by baseline sCD14 tertile by additionally adjusting for the sCD14 tertile main effect and the study arm by sCD14 tertile interaction.

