4.1 Analysis Populations

Intent-To-Treat (ITT): All randomized participants.

Modified Intent-To-Treat (mITT): All randomized participants who started study product.

Per-Protocol (PP): All eligible, randomized participants who 1) have baseline and week 25/26 sCD14 measurements, 2) remain on study product through week 26 (participants with more than 50% on average of missed study product may be excluded), 3) have not used prohibited medications, 4) do not have a confirmed virologic failure (as defined per section 6.2.3 at or prior to week 26, and 5) do not experience inflammatory conditions, receive vaccines, or have concurrent illness (as defined per section 6.2.3).

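### Does leaving the ITT set unassigned in SAP 4.4, with no stated rule for participants who have neither a week 25 nor a week 26 sCD14, leave the trial without its promised ITT check?

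*SAP*

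**What the plan says.** Protocol 9.6 limits the main analysis to an as-treated set: participants with baseline and week 26 sCD14 who stayed on product and had no prohibited medication, confirmed virologic failure or intercurrent inflammatory condition. It then adds: "A supplemental intent-to-treat analysis will also be performed and will include all randomized participants". The same section says "Measurements obtained while inflammatory conditions are present will not be included in the analysis". Protocol 9.6.1 sets the model for the change in sCD14: "The only predictor variable will be study arm".

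SAP 4.1 defines three sets, among them "Intent-To-Treat (ITT): All randomized participants". Its per-protocol (PP) definition carries a discretionary adherence clause: "participants with more than 50% on average of missed study product may be excluded".

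SAP 4.4 assigns safety to the modified ITT set and correlations to PP. Its tables and graphs for continuous outcomes cover cross-sectional values and "change from baseline to post-baseline study weeks and will use the PP population". The next sentence, on comparing mean changes between arms, names no population. The only supplemental analyses it lists for the primary endpoint are baseline adjustment and the baseline-tertile interaction.

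On missing values, Protocol 9.6 and SAP 4.3 agree that one draw is used alone when its pair is missing. Neither says what happens in the ITT comparison when both week 25 and week 26 are missing. On follow-up, Protocol 6.2.4 says of those who stop product early: "Participants who prematurely permanently discontinue study treatment will be followed on study/off study treatment per the SOE". Of those who never start it, the protocol says: "All CRFs must be completed and keyed for the period up to and including week 2".

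**The concern.** The ITT comparison is the only planned check on whether selection into the PP set moved the sCD14 result. That set depends on events after randomisation and on an adherence exclusion that may or may not be applied. The SAP is the document that should turn the protocol's promise into an analysis, yet its methods section never uses the ITT set. Someone programming from SAP 4.4 alone could produce a PP result and nothing else.

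The second worry is missing outcomes. An analysis of every randomised participant cannot be met from observed data if some have no end-of-treatment value. The protocol expects losses: Protocol 9.4 inflates the sample by 20%, from 36 to 45 per arm. If the handling rule is chosen after sCD14 results are known and the choice alters the answer, the check would itself depend on the data.

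**Working it through.** **1. The plan's own figure.** Protocol 9.4 gives a difference of 0.07 log10, SD of change 0.09, two-sided alpha 0.05 and 90% power. A two-sample t-test calculation gives n = 35.73, so 36 per arm. Then 36 / (1 - 0.20) = 45 per arm, or 90 in total. The stated size is reproduced. Power is 90.2% at 36 per arm and 95.4% at 45.

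**2. What the documents yield together.**

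| Element of the ITT comparison | Where it is settled |
|---|---|
| That it is done | Protocol 9.6; nothing in the SAP withdraws it |
| Who is in it | SAP 4.1 |
| Outcome and model | Protocol 9.6.1: change in sCD14, arm only |
| Off-treatment week 25/26 values | SAP 4.3 classifies them, and limits the on-treatment restriction to per-protocol analyses |
| Windows, including for a draw at premature discontinuation | SAP 4.3, stated for all analyses: weeks 23 to 28 |
| Samples near influenza vaccination or during inflammation | SAP 4.4 and Protocol 9.6, neither limited to PP |
| One of two draws missing | Protocol 9.6 and SAP 4.3: use the single value |
| Both draws missing | Not stated |

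Only the last row is open. With no imputation method written anywhere, the default is to analyse those with an observed change.

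**3. Does the open row matter?** Illustrative assumptions: 9 of 45 per arm lack both draws (the whole 20% allowance), SD 0.09, placebo mean change 0, no auxiliary data. Negative favours the active arm.

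Observed data: SE = 0.09 × √(2/36) = 0.0212 on 70 df. For d = -0.050, t = -2.36 and p = 0.021. For d = -0.070, t = -3.30 and p = 0.0015.

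Multiple imputation, pooled by Rubin's rules:

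| Handling of missing values | Estimate, d = -0.050 | p | Estimate, d = -0.070 | p |
|---|---|---|---|---|
| Observed data only | -0.050 | 0.021 | -0.070 | 0.0015 |
| Imputed within arm | -0.050 | 0.023 | -0.070 | 0.0017 |
| Missing active values drawn from placebo | 0.8 × d = -0.040 | 0.06 to 0.07 | -0.056 | 0.011 to 0.013 |
| Within arm, active shifted by +0.07 | d + (9/45) × 0.07 = -0.036 | about 0.10 | -0.056 | 0.013 |

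The ranges reflect details of the imputation. The two ordinary choices agree. The last two rows are stress tests. At d = -0.050, the +0.07 shift puts missing active participants 0.07 - 0.05 = 0.02 above the placebo mean, that is, worse than placebo.

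**4. Is 9 of 45 realistic?** Protocol 9.4 intends the 20% for laboratory problems and loss to follow-up. One surviving draw is enough, and those who stop product stay on the visit schedule, so fewer should lack both draws. With 4 of 45, the +0.07 shift moves the estimate by (4/45) × 0.07 = 0.006.

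**The case for a change.** The strongest case for a change is that the omission is real and cheap to repair. SAP 4.4 counts its supplemental analyses of the primary endpoint as two, and ITT is not one of them. Because the main analysis is as-treated, the ITT check matters more than usual. Stored samples are assayed only after follow-up ends (SAP 2.11.2), so a rule could be fixed before any sCD14 result exists. Participants who never start product belong to the ITT set and may well have no late sample. Under the stress tests, significance is lost at an observed difference of -0.050, and with the +0.07 shift up to about -0.057.

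What stands: the ITT set is not assigned in SAP 4.4, the both-missing case is unwritten, and one sentence would make the SAP tidier.

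What does not: that the SAP as written delivers only a PP result. The sentence in SAP 4.4 that names PP governs summaries, the between-arm sentence names no set, and the off-treatment rules in SAP 4.3 would have little purpose if every sCD14 comparison were PP. Nor is it certain that non-starters have no value. The protocol requires their forms through week 2 but does not waive later visits, whereas the substudy (A5352s 6.2.3) says explicitly when no follow-up is required. The loss of significance arises only under handling rules that neither document proposes. The discretionary adherence clause concerns the definition of PP and is a separate matter.

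**Conclusion.** No change to the plan follows. This is a gap in the specification of a supplemental analysis that analysts can fill from the two documents: compare all randomised participants with an observed change, as randomised, with arm as the only predictor and with on- and off-treatment values under SAP 4.3. Ordinary reporting would show how many in each arm lack both draws.

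No rule the plan states is shown to give a wrong result, and the as-treated primary analysis is untouched because its set already excludes participants without an end-of-treatment value. Under the assumed 9 of 45 missing per arm, the two ordinary ways of handling the gap give the same estimate and nearly the same p-value. The largest shift under the stress tests is 0.014 log10, or 0.014 / 0.07 = 20% of the target difference, and it falls to 0.006 with 4 of 45. These sizes rest on assumed missingness, the protocol's SD of 0.09 and no use of the week 6 and week 14 values. The conclusion would be weaker if many more participants in one arm than in the other lacked both draws, which the documents give no reason to expect.

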# 1.2 Secondary Hypotheses

- 1.2.1 After administration of Visbiome Extra Strength, other markers of systemic inflammation interleukin (IL)-6, interferon gamma-induced protein (IP)-10, soluble tumor necrosis factor receptor I (sTNF-RI), soluble CD163 (sCD163), oxidized low-density lipoprotein (LDL), kynurenine to tryptophan (KT) ratio, and coagulopathy (D-dimer) will decrease.
- 1.2.2 After administration of Visbiome Extra Strength, markers of microbial translocation lipopolysaccharide (LPS) and lipopolysaccharide-binding protein (LBP) will decrease.
- 1.2.3 After administration of Visbiome Extra Strength, peripheral CD4+ lymphocyte counts and CD4+/CD8+ ratio will increase.
- 1.2.4 After administration of Visbiome Extra Strength, markers of lymphocyte and monocyte activation and senescence will decrease.
- 1.2.5 Visbiome Extra Strength administration will increase gastrointestinal microbial diversity in fecal samples.
- 1.2.6 After administration of Visbiome Extra Strength, markers of enterocyte death as measured by I-FABP (intestinal fatty acid binding protein) will decrease.
- 1.2.7 Visbiome Extra Strength will be safe and well tolerated.
- 1.2.8 The gut microbiome changes will persist after completion of Visbiome Extra Strength administration.

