# 1.3 Exploratory Hypotheses

- 1.3.1 After administration of Visbiome Extra Strength, insulin sensitivity, as measured by homeostatic model assessment (HOMA-IR), will improve.
- 1.3.2 After administration of Visbiome Extra Strength, fasting lipid parameters will improve.
- 1.3.3 After administration of Visbiome Extra Strength, changes in gut microbiome will be associated with changes in markers of systemic inflammation and coagulation as well as changes in cellular immune activation markers.

- 1.3.4 After administration of Visbiome Extra Strength, changes in markers of microbial translocation will be associated with changes in systemic markers of inflammation and coagulation as well as changes in cellular immune activation markers.
- 1.3.5 The improvements in markers of systemic inflammation and microbial translocation will persist for 12 weeks after completion of 24 weeks of Visbiome Extra Strength.
- 1.3.6 At baseline, the composition of the microbiome will differ by antiretroviral class including protease inhibitors (PIs), nonnucleoside reverse transcriptase inhibitors (NNRTIs), and integrase inhibitors (InSTIs).
- 1.3.7 After administration of Visbiome Extra Strength, gastrointestinal symptom scores will improve.
- 1.3.8 The composition of the microbiome will be influenced by dietary intake as reported through the dietary assessments.

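### Correlations between marker changes are planned without regard to arm; if the product moves both markers, a pooled Spearman coefficient mixes the shared arm effect with any participant-level link

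*SAP*

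**What the plan says.** SAP 4.4 gives the whole correlation method in one sentence: "Correlations will be assessed with scatter plots as well as the Spearman correlation coefficient and associated p-value using the PP population". Protocol 9.6.2 says which quantities are correlated: "Spearman correlations will be used to evaluate correlations between changes in select outcome measures". Neither sentence mentions study arm.

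SAP 4.1 defines the PP population as "All eligible, randomized participants who 1) have baseline and week 25/26 sCD14 measurements", followed by conditions on treatment, medication, virology and illness. None of these refers to arm, so both arms are in the set.

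Elsewhere in SAP 4.4, arm is named where it is meant to enter: in the adverse event comparison, the comparison of mean changes, and the baseline-tertile interaction. The adjusted regression offered there serves the comparison of mean changes only.

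The correlations serve exploratory hypotheses 1.3.3 ("changes in gut microbiome will be associated with changes in markers of systemic inflammation and coagulation") and 1.3.4 ("changes in markers of microbial translocation will be associated with changes in systemic markers of inflammation and coagulation"), with matching objectives 1.6.3 and 1.6.4. On testing, SAP 4.4 states: "All statistical tests will be two-sided with a nominal alpha level of 0.05 and no adjustment for multiple testing".

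**The concern.** The protocol expects the product to move the markers that are to be correlated. Protocol 1.2.2 predicts that "markers of microbial translocation lipopolysaccharide (LPS) and lipopolysaccharide-binding protein (LBP) will decrease"; 1.1 and 1.2.1 predict falls in sCD14 and the other inflammation and coagulation markers.

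If two changes both shift with arm, treated participants tend to lie towards one end of both scales and placebo participants towards the other. The pooled rank correlation is then non-zero even if, within each arm, one change carries no information about the other. Such a result only repeats that both markers responded to the product, which the planned arm comparisons already show.

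What is at stake is interpretation. A reader shown a coefficient and a p-value will tend to conclude that participants whose translocation markers fell more also had larger falls in inflammation. The pooled coefficient does not separate that statement from the arm effect, and the confusion grows with the size of the product's effect.

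**Working it through.** **Inputs.** From Protocol 9.4: 36 evaluable participants per arm; planned sCD14 effect 0.07 log10 with SD of change 0.09; detectable effects for secondary endpoints of 0.77, 0.67 and 0.59 SD at 90%, 80% and 70% power. From Protocol 9.3: 1:1 allocation. From SAP 4.4: two-sided 5% level, no multiplicity adjustment. The documents give no sample size or power figure for the correlations.

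**The plan's own figures.** The normal approximation gives n per arm = 2 × (1.960 + 1.282)² × 0.09² / 0.07² = 34.7, so 35. The two-sample t-test gives 35.7, so 36. Then 36 / 0.8 = 45 per arm, 90 in total, as stated. With 36 per arm the t-test has power 89.6%, 80.1% and 69.5% for 0.77, 0.67 and 0.59 SD, and the confidence interval half-width is 0.47 SD. All agree with the protocol.

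**Pooled correlation from arm shifts alone.** Let the within-arm correlation be zero and let the arms differ by d1 and d2 (in within-arm SDs) on the two changes. With 1:1 allocation the between-arm covariance is d1·d2/4 and each variance is 1 + d²/4, so the pooled Pearson correlation is

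r = (d1·d2/4) / √[(1 + d1²/4)(1 + d2²/4)].

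For d1 = d2 = 0.77: r = 0.1482 / 1.1482 = 0.129. If either shift is zero, r = 0.

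**Approximate rejection rate at 0.77 SD.** By Fisher's z, atanh(0.129) × √(72 − 3) = 0.1297 × 8.307 = 1.08. The upper-tail chance is P(Z > 1.96 − 1.08) = P(Z > 0.88) ≈ 0.19.

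**Simulation.** 40,000 runs per scenario, bivariate normal changes, 36 per arm, zero within-arm correlation. Partial Spearman was computed by ranking all participants, subtracting each arm's mean rank and correlating the remainders (t with 69 df).

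| Shift, marker 1 / marker 2 (SD) | Mean pooled rho | Pooled test rejects | Partial Spearman given arm rejects |
|---|---|---|---|
| 0 / 0 | 0.00 | 4.9% | 4.9% |
| 0.77 / 0 | 0.00 | 5.0% | 4.9% |
| 0.40 / 0.40 (assumed) | 0.04 | 6.1% | 4.9% |
| 0.59 / 0.59 | 0.08 | 10.2% | 4.9% |
| 0.67 / 0.67 | 0.10 | 13.1% | 5.0% |
| 0.77 / 0.77 | 0.13 | 19.2% | 5.1% |
| 1.0 / 1.0 (assumed) | 0.20 | 40.8% | 4.9% |

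The Monte Carlo standard error at 19.2% is √(0.192 × 0.808 / 40,000) = 0.2 percentage points. At the planned sCD14 effect for both markers (0.07 / 0.09 = 0.78 SD) the pooled rate is 19.6%.

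**Cost of adjusting.** With a true within-arm correlation of 0.4 and both shifts at 0.77 SD, the pooled test rejects in 98.5% of runs, partial Spearman in 90.9%, and Spearman in one arm alone (n = 36) in 64.0%.

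**The case against.** Several objections stand and limit the point.

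- **Pooling is not an express rule.** Naming the PP population fixes who is analysed, not whether the arms are combined. Both hypotheses open with administration of the product ("After administration of Visbiome Extra Strength, changes in gut microbiome will be associated with changes in markers of systemic inflammation"), which could suit an analysis of the treated arm. Pooling is the natural reading of a silent text, and a programmer following it would pool.
- **A pooled rejection is not wrong in itself.** A reader might infer that the trial will produce false-positive results on mechanism. The documents do not support that. The hypotheses speak of association and the objectives of exploring correlations. If both markers shift with arm, the changes are truly associated across the whole sample. The error would lie in reading that as a link beyond the shared arm effect.
- **Inflation is conditional.** There is none if only one marker moves. The 0.77 SD in Protocol 9.4 is a detectable effect, not a forecast. No shift is forecast for LPS, LBP, diversity or cellular markers, and Protocol 2.1 reports that sCD14 and D-dimer were fairly stable in the HIV pilot study. Rates of 40% or more rest on assumed shifts.
- **Masking of a true association** can be constructed by giving the arm shifts the opposite sign to the within-arm correlation. The protocol expects translocation and inflammation markers to fall together, and diversity to rise as inflammation falls. In both cases the signs agree, so the plan does not imply masking.
- **Coverage of 1.3.3 is uncertain.** SAP 3.2 and 3.3 mark the microbiome diversity outcomes as not analysed at the Statistical and Data Analysis Center (SDAC), so SAP 4.4 may not govern those correlations. Protocol 9.6.2 carries no such limit.

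The objectives are exploratory, and scatter plots are already planned. Even so, p-values are to be reported at a nominal 5%, and the text leaves the handling of arm open.

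**Conclusion.** The plan does not say how arm enters the correlations of changes and, read literally, it pools. Where the product moves both markers, the pooled coefficient cannot be taken as a participant-level link. With 36 per arm and no within-arm correlation, the chance of a nominally significant pooled result rises from 5% to about 10% at 0.59 SD and 19% at 0.77 SD in both markers. Adjusting for arm holds it at about 5%. These figures assume normally distributed changes, equal arms and equal shifts in the two markers.

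The consequence is confined to exploratory objectives: firmly 1.6.4 (hypothesis 1.3.4), less certainly 1.6.3 (hypothesis 1.3.3). The primary analysis and the secondary arm comparisons are untouched. This is an inexpensive improvement to an under-specified analysis. It does not show that a wrong analysis has been prescribed or that a spurious result is certain.

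**What to change.** In SAP 4.4 and Protocol 9.6.2, state that correlations between changes will be reported as partial Spearman coefficients adjusted for arm, or as within-arm coefficients combined across arms, beside any pooled value. Mark arm on the scatter plots. State that conclusions about links between changes rest on the arm-adjusted estimate. Correlations of baseline values may stay pooled. Say also whether the same rule applies to the microbiome correlations done outside SDAC.

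The cost is a change of wording and a few lines of code, with no new data. The downside is somewhat lower power when the arm shift and the within-arm association have the same sign: about 91% against 99% at a within-arm correlation of 0.4 and shifts of 0.77 SD. Part of the pooled figure comes from the arm shift itself. Adjusting across both arms is preferable to analysing the treated arm alone, which has 64% power in the same setting.
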